#### **4.2.5.2 Deaths**

All deaths recorded on the disposition page, the AE page, or SAE page (with a death date, cause of death, outcome or SAE categorization present) of the CRF will be considered a death in the analyses. Any deaths that occur during the study will be described in depth as narrative in the CSR. A listing of all deaths that occur during the study will be produced.

#### **4.2.5.3 Clinical laboratory variables**

Unless otherwise specified, laboratory data obtained after the start of open-label study medication dosing up to and including 4 days (30 days for liver function laboratory tests) after the last open-label study medication dosing date (or up to the start of the double-blind treatment period, whichever date comes first) will be considered as obtained during the open-label treatment period. Similarly, laboratory data obtained after the start of study medication dosing up to and including 4 days (30 days for liver function laboratory tests) after the last double-blind dosing date will be considered as obtained during the double-blind treatment period.

All analyses of laboratory data will be performed in both Conventional Units (CV) and Standard International Units (SI).

Listings for lab data include everything in the database.

#### **Marked Laboratory Abnormalities**

Laboratory abnormalities will be evaluated based on laboratory values meeting pre-defined MAs criteria, as per criteria defined in Appendix 2. The number and percent of subjects with MAs occurring during the double-blind treatment period will be summarised by treatment group and laboratory test. In addition to the primary analysis, a sensitivity analysis of MAs will be performed that excluded data after rescue. To capture all possible drug related liver elevations, liver MA summaries included data up to 30 days after the last dose of double-blind treatment.

An additional summary of laboratory MAs will be presented for the open-label treatment period based on comparison of laboratory values with the baseline value for the open-label treatment period.

#### **Change from Baseline for Selected Laboratory Parameters Over Time**

Values and changes from baseline at each scheduled time point for clinical laboratory parameters, including serum creatinine, and eGFR by MDRD, will be summarised by treatment group using descriptive statistics for double-blind treatment period.

There will be no imputation for missing values. However, assessment values of the form “<x” (i.e. below the lower limit of quantification) or “>x” (i.e. above the limit of quantification) will be imputed as “x” in the calculation of summary statistics but displayed as “<x” or “>x” in the listings.

#### **4.2.5.4 Vital signs**

Values and changes from baseline at each scheduled time point for vital signs, including seated blood pressure and heart rate, will be summarised by treatment group using descriptive statistics for double-blind treatment period.

#### **4.2.5.5 Electrocardiograms**

The normality/abnormality of the ECG tracing, as determined by the investigator, will be summarised using shift table to present baseline and Week 24 value. When the data at Week 24 is not available for a discontinued subject, then the last observation before discontinuation of that subject (regardless of rescue) will be used for summary.

### **4.3 China Cohort**

Per China Regulatory Authority guidance, in addition to the evaluation of global cohort data for primary, secondary and selected exploratory plus safety objectives, evaluation of consistency in efficacy and safety in China is required to facilitate the benefit-risk assessment for China cohort, defined as subjects in China sites. Therefore, the following data will be presented for the China Cohort using the same analysis methods as outlined in section [4.1](#) and [4.2](#).

- subject disposition
- demographics and baseline characteristics
- medical history
- extent of exposure and treatment compliance
- primary, secondary and selected exploratory efficacy endpoints
- safety endpoints including AEs/SAEs, AESI, Clinical laboratory tests, ECG and Vital signs

The same definition of analysis sets outlined in section [2.1](#) will be applied in China cohort. All efficacy analysis will be considered as exploratory objective for China cohort. A nominal p-value will be provided for the purpose of the completeness of the data analysis. Sensitivity analysis for the primary endpoint might be conducted for China Cohort. For the subgroup analysis in China Cohort, if the value of the grouping variable cannot be determined, the patient will be excluded from the corresponding subgroup analysis. For each subgroup analysis, if, in any treatment group, the number of patients is less than 10 for a subgroup, this subgroup will not be included in the interaction model and descriptive summaries only will be displayed.

### **4.4 Early termination analyses**

On Jun 30, 2020 AstraZeneca decided to stop commercialization of QTERNMet/Qtrilmel and to withdraw all active licenses, for business reasons. DS-NAVIGATION will be closed without recruiting subjects in China and patients recruited from Thailand and Vietnam will complete the study.

Therefore, the planned analyses in this study will be conducted over all data available. To support the synopsis format CSR, the following analysis will be performed:

- Summaries of subject disposition, summaries in the Enrolled subjects set and Open-label treated subjects analysis set, as described in Section 4.2.1. Subject disposition will also be listed.
- Summary of analysis set, defined in Section 2.1.
- Demographic and baseline characteristics as described in Section 4.2.2 and Section 4.2.2.1.
- An overall summary of adverse events at subject level, including TEAEs, TESAEs, death, hypoglycaemia, severe events, treatment-related events, events leading to the discontinuation of study medication, events leading to death will be presented for open-label treatment period and double-blind treatment period. TEAEs will also be summarised by SOC and PT in open-label and double-blind treatment. TESAEs will be summarised by SOC and PT in the double-blind period only. AEs and SAEs will also be listed.
- Important protocol deviations, observed HbA1c data, and marked abnormalities by test will be listed.

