#### **8.5.7 Safety analysis**

Safety analyses for the double-blind treatment period will be performed using the Safety analysis set, including data after rescue. Safety analyses will include, where appropriate, descriptive statistics, counts and percentages for AEs and other safety measures. No formal statistical tests will be performed.

The number and percent of subjects with at least one AE will be summarized for each treatment group, including summaries of AEs, SAEs, AEs leading to discontinuation, and AEs of special interest. Summaries will include the number of subjects with events by specified system organ classes and preferred terms.

Additionally, the incidence of AEs and frequency of recurring AEs will be summarized for each treatment group for both frequent events and for selected AEs of special interest.

Values and changes from baseline at each scheduled time point for clinical laboratory parameters and vital signs, including seated BP and HR, will be summarized by treatment group using descriptive statistics. The normality/abnormality of ECG tracings, as determined by the investigator, will be summarized by shift tables overall and by ECG tracing at baseline. The number and percent of subjects with laboratory values meeting marked abnormality criteria will be summarized for each treatment group. Other safety assessments including Scr and eGFR by MDRD, will be summarized by treatment group using descriptive statistics of values and changes from baseline at each scheduled time point.

Additional analyses for AEs and laboratory marked abnormalities may be performed excluding data after rescue and study treatment discontinuation. The primary analyses of events of hypoglycaemia will be performed excluding data after rescue and study treatment discontinuation.

Selected safety analyses will be performed for the open-label treatment period using the Open-label treated subjects analysis set.

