- Open-label period treatment emergent hypoglycemia: date of first dose of study medication during open-label period  $\leq$  hypoglycemia onset date  $\leq$  minimum (date of last dose of study medication during open-label treatment period +4 days, date of first dose of study medication during the double-blind treatment period – 1 day) or minimum (date of last dose of study medication during open-label treatment period +30 days, date of first dose of study medication during the double-blind treatment period – 1 day) if SAE
- Double-blind period treatment emergent hypoglycemia: date of first dose of study medication during double-blind treatment period  $\leq$  hypoglycemia onset date  $\leq$  date of last dose of study medication during double-blind treatment period +4 days or date of last dose of study medication during double-blind treatment period +30 days if SAE

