## 4.2.5 Safety analyses

Safety analysis, including adverse Events (AEs) and laboratory marked abnormalities (MA), for open-label treatment period will be conducted using open-label treated subjects analysis set.

Safety analyses of the double-blind treatment period will be performed using safety analysis data set, including data after rescue (primary safety analysis). Additional sensitivity analyses for AEs and laboratory MA will be performed excluding data after rescue for the double-blind treatment period. The primary analyses of events of hypoglycaemia will be performed excluding data after rescue.

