### All Adverse Events

An overall summary of adverse events at subject level, including TEAEs, TESAEs, death, hypoglycaemia, severe events, treatment-related events, events leading to the discontinuation of study medication, events leading to death will be presented for open-label treatment period, double-blind treatment period and double-blind treatment period prior to rescue, respectively.

All TEAEs (serious and non-serious, excluding hypoglycaemic events that are not reported as SAEs) will be summarised by SOC and PT for double-blind treatment period. In addition, a subject listing of all reported AEs will be produced, displaying all events including pre-treatment AEs and post-treatment AEs, if any. All TEAEs (serious and non-serious) including all hypoglycaemic events will also be summarised by treatment group, where applicable.

In addition, the following summaries will be provided for the double-blind treatment period (excluding hypoglycaemic events that are not reported as SAEs):

- Most common TEAE by PT and treatment group (i.e., reported by  $\geq 2\%$  of subjects in any treatment group),
- TEAEs by SOC, PT, intensity and treatment group,
- TEAEs related to study medication (by investigator) by SOC, PT and treatment group.
- Proportion of subjects with TEAEs by SOC and PT in subgroups of subjects defined by age category ( $< 65$  and  $\geq 65$  years), gender and race.

No formal comparisons will be made between treatments. No formal statistical testing will be performed, only summary statistics will be provided.

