## Hypoglycaemic Events

Separate pages to capture events of hypoglycaemia are contained within the CRF.

Hypoglycaemic events with an onset from Day 1 of double-blind treatment to and including 4 days after the last dose date of double-blind treatment will be considered as occurring during the double-blind treatment period. The proportion of subjects with hypoglycaemic events will be tabulated by treatment group.

Hypoglycaemia episodes will be categorised according to the American Diabetes Association (ADA) Criteria [\[ADA 2018\]](#) which classifies hypoglycaemia as follows:

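### The hypoglycaemia line kept by SAP 4.4 includes events after rescue, although the protocol and SAP make the analysis without them primary

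*SAP*

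**What the plan says.** SAP 4.2.5 sets the general rule that double-blind safety analyses are run "including data after rescue (primary safety analysis"). It then makes an exception: "The primary analyses of events of hypoglycaemia will be performed excluding data after rescue". Protocol 8.5.7 makes the same exception and goes one step further: "The primary analyses of events of hypoglycaemia will be performed excluding data after rescue and study treatment discontinuation".

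SAP 4.2.5.1 (All Adverse Events) planned an overall subject-level summary, with hypoglycaemia as one of its items, which "will be presented for open-label treatment period, double-blind treatment period and double-blind treatment period prior to rescue, respectively". SAP 4.2.5.1 (Hypoglycaemic Events and Table 4) added dedicated outputs: counts of subjects and events, a summary by ADA class, and a listing of every event with its class.

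SAP 4.4 was added after the sponsor stopped the programme for business reasons. It repeats the overall summary, still with hypoglycaemia, but there the items through "events leading to death will be presented for open-label treatment period and double-blind treatment period". It names no pre-rescue panel and none of the dedicated hypoglycaemia outputs. SAP Section 6 confines the work to what 4.4 contains.

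**The concern.** The plan singles out hypoglycaemia as the safety outcome for which post-rescue data should not drive the main result. The reason is easy to see in the protocol. The Synopsis allows insulin as rescue, Section 1.1 links insulin to a high risk of hypoglycaemia, and Section 1.4 keeps rescued subjects in the double-blind period on study drug. A count over the whole period can therefore mix events on randomised treatment alone with events on randomised treatment plus rescue.

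If the abbreviated report shows only the whole-period count, it reports an adverse event of special interest on the scope that the plan treats as non-primary, and nothing tells the reader so. What is at stake is the transparency of one descriptive line. No hypothesis test or efficacy conclusion depends on it.

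**Working it through.** There is no plan figure to reproduce, so the check sets the planned outputs beside the retained ones.

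**1. Which scope is primary?** Protocol 8.5.7 and SAP 4.2.5 agree that for hypoglycaemia it is the scope that excludes post-rescue data.

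**2. What was planned, and what is kept?**

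| Output | Planned (SAP 4.2.5.1) | Kept (SAP 4.4) |
|---|---|---|
| Overall summary, open-label | yes | yes |
| Overall summary, double-blind | yes | yes |
| Overall summary, double-blind before rescue | yes | no |
| Hypoglycaemia subject and event counts | yes | no |
| Hypoglycaemia by ADA class | yes | no |
| Hypoglycaemia event listing with ADA class | yes | no |

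Of three panels in the overall summary two remain, and the one removed is the pre-rescue panel.

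**3. Does the retained double-blind line stop at rescue?** Two passages indicate that it does not. SAP 4.2.5.1 lists the double-blind and pre-rescue panels separately, so the plain one must cover the whole period. SAP 3.5.1 defines double-blind treatment-emergent hypoglycaemia from first dose to last dose "during double-blind treatment period +4 days or date of last dose of study medication during double-blind treatment period +30 days if SAE", without mention of rescue.

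**4. Does the opening of 4.4 restore the primary version?** It says that the planned analyses will be run on all available data. The list that follows and Section 6 then restrict the work to the listed items, and the pre-rescue analysis is not among them.

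**5. Can a reader rebuild it from the retained listings?** SAP 4.2.5.1 keeps hypoglycaemia off the adverse event page unless it is serious, so the AE and SAE listings do not carry non-serious events. The rescue-medication listing planned in SAP 4.2.3.1 is not kept either. The marked-abnormality listing holds laboratory glucose values (Appendix 2), not reported episodes.

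**6. Secondary check: the rule after treatment ends.**

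| Place | Rule for double-blind hypoglycaemia |
|---|---|
| Protocol 8.5.7 (primary analysis) | excludes data after rescue and after treatment discontinuation |
| SAP 4.2.5 (primary analysis) | excludes data after rescue; silent on discontinuation |
| SAP 3.5.1 (treatment-emergent) | last dose + 4 days; + 30 days if serious |
| SAP 4.2.5.1, Hypoglycaemic Events | "to and including 4 days after the last dose date of double-blind treatment" |

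For serious hypoglycaemia the two SAP windows differ by 30 − 4 = 26 days. Protocol 3.9.3 leaves diabetes medication after discontinuation to the investigator, so the longer window can take in events on other drugs. Section 6 does not mention this difference.

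**The case against.** The strongest reply is that the reduction is deliberate and disclosed. SAP 4.4 gives the reason and the report format, Section 6 says that the other analyses will not be done, and the amendment history logs both. The same decision drops the primary efficacy model and the tables for adverse events of special interest. This stands: the lost panel follows from an open, general decision. Section 6 does not, however, name the loss, and the surviving line carries no label.

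Second, SAP 4.2.5 contains both the general rule and the hypoglycaemia exception, and 4.4 does not say which governs its line. A reader could let the line inherit the exception. The separate panels and the definition in 3.5.1 argue against that. If the reader is still unsure, the line is ambiguous and needs a label all the same.

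Third, not every window difference is a conflict. For HbA1c, SAP 4.2.4.2 treats values up to 8 days after last dose as on treatment, and the 4 days for hypoglycaemia can be read as a similar carry-over. The Hypoglycaemic Events outputs are also dropped, so 3.5.1 alone governs the retained line. Both points stand. They leave the 30-day extension for serious events and the discontinuation clause missing from SAP 4.2.5.

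Two stronger readings are tempting. A reader might infer that the overview line is the only retained place where non-serious hypoglycaemia appears. One planned table does leave it out: "All TEAEs (serious and non-serious, excluding hypoglycaemic events that are not reported as SAEs) will be summarised by SOC and PT". But the same section also plans a TEAE summary with all hypoglycaemic events, and 4.4 does not say which version its table by SOC and PT follows. A reader might also infer heavy contamination because rescue is possible from Week 6 onwards. That only bounds the post-rescue time of a subject who is rescued; it says nothing about how many were or how many events they had.

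**Conclusion.** The point holds as a minor one. Under SAP 4.4 the double-blind hypoglycaemia line is reported on a scope that includes post-rescue events, while the protocol and SAP make the scope without them primary, and the retained AE and SAE listings do not allow the primary version to be recovered. This rests on reading the plain double-blind panel as the whole period, which the panel structure and the definition in 3.5.1 support.

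Size and direction are unknown. The documents give no rescue counts, no hypoglycaemia counts and no number randomised. The plan foresaw about 23 subjects per arm outside China, so 3 × 23 = 69 of 342, and 4.4 says that the study closes without recruiting in China; the group is therefore likely to be small. If no randomised subject was rescued, the rescue issue changes nothing. The documents support neither a claim that safety conclusions are distorted nor a claim that the reduction was concealed.

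The unreconciled treatment of events after discontinuation is a secondary inconsistency. Early termination does not explain it.

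**What to change.** 1. In SAP 4.4, present the double-blind hypoglycaemia line before rescue as well, by restoring that panel from SAP 4.2.5.1 for this line. Alternatively, add the hypoglycaemia listing already specified there, with onset date, ADA class and a flag for before or after first rescue.
2. Label the existing double-blind line as including post-rescue events.
3. Reconcile protocol 8.5.7, SAP 4.2.5, SAP 3.5.1 and the Hypoglycaemic Events text on data after treatment discontinuation and on the window for serious events. Record any departure from the protocol in SAP Section 6.

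The panel and the listing are already specified. The events are on the hypoglycaemia eCRF pages (protocol 5.2.5.1), and rescue use was to be summarised and listed (SAP 4.2.3.1), so no new data are needed. The cost is one extra panel or short listing in an abbreviated report, a label, and a sentence or two in Sections 4.4 and 6.

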## **5. INTERIM ANALYSES (NOT APPLICABLE)**

## **6. CHANGES OF ANALYSIS FROM PROTOCOL**

Due to early termination for business reasons, the analyses planned in this study will not be performed as planned, all but the analyses in Section 4.4.

## 8. APPENDIX

### 8.1 Appendix 1 – IPD MASTER LIST

IPD code	IPD Category	Explanation	PP Relevant IPD	Exclusion level
1. Inclusion Criteria Deviations: for subject who did not meet any of below criteria (refer to CSP section 3.1)				
1.1	Did not fulfil eligibility criteria	Subjects must be willing and able to give signed and dated written informed consent		
1.2	Did not fulfil eligibility criteria	
a. For inclusion into open-label treatment period of Stratum A Subjects with T2DM with inadequate glycaemic control, defined as central laboratory HbA1c <math>\geq 8.0\%</math> and <math>\leq 11.5\%</math> obtained at the screening visit (i.e.. Week -18), on stable metformin therapy alone at a dose <math>\geq 1500\text{mg}</math> per day or a maximal tolerated dose for at least 8 weeks prior to screening visit
 
b. For inclusion into open-label treatment period of Stratum B Subjects with T2DM with inadequate glycaemic control, defined as central laboratory HbA1c <math>\geq 7.0</math> and <math>\leq 10.5\%</math> obtained at the screening visit (i.e.. Week -10), on stable metformin therapy at a dose <math>\geq 1500\text{mg}</math> per day or a maximal tolerated dose AND a DPP-4 inhibitor (free form combination) at the maximum approved dose for at least 8 weeks prior to screening visit
 
c. For inclusion into double-blind treatment period of both Stratum A and B Subjects with T2DM with inadequate glycaemic control defined as central laboratory HbA1c <math>\geq 7.0</math> and <math>\leq 10.5\%</math> obtained at the Week -2 visit of the open-label treatment period
 
d. Body mass index (BMI) <math>\leq 40.0\text{kg/m}^2</math> at the screening visit.
	
1. Randomised subjects without Type II diabetes or with central laboratory HbA1c at screening and/or -2 week outside of specified limits such as more than 0.2% outside of specified limits (i.e. violation of inclusion criterion # 2c or screening HbA1c value out of range specified in 2a or 2b)
 
2. Randomised subjects who do not receive stable dose of metformin as of the start of open-label (i.e. Violation of inclusion criterion 2a and 2b)
	Completely Exclude from PP analysis set

IPD code	IPD Category	Explanation	PP Relevant IPD	Exclusion level
1.3	Did not fulfil eligibility criteria	
Age and Reproductive Status
 
a. Men and women, aged <math>\geq 18</math> years old at time of screening visit
 
b. Women of childbearing potential (WOCBP) must have a negative serum pregnancy test at screening and negative urine pregnancy test within 24 hours prior to the start of IP. WOCBP must be using an acceptable method of contraception to avoid pregnancy throughout the study and for at least 4 weeks after the last dose of study medication in such a manner that the risk of pregnancy is minimized
		
2. Exclusion Criteria Deviations: for subject who met any of below criteria (refer to CSP section 3.2)				
2.1	Did not fulfil eligibility criteria	
Target Disease Exceptions
 
a. History of diabetes insipidus and type 1 diabetes
 
b. Symptoms of poorly controlled diabetes that would preclude participation in this trial including but not limited to marked polyuria and polydipsia with greater than 10% weight loss during 3 months prior to screening
 
c. History of hyperosmolar nonketotic coma
 
d. History of DKA requiring medical intervention (e.g. emergency room visit and/or hospitalization) within 1 month prior to screening
 
e. Subjects age <math>< 40</math> years with positive GAD antibodies.
		
2.2	Did not fulfil eligibility criteria	
Medical History and Concurrent Diseases
 
a. History of bariatric surgery or lap-band procedure within 12 months prior to screening
 
b. Any unstable endocrine, psychiatric or rheumatic disorders as judged by the investigator
		

IPD code	IPD Category	Explanation	PP Relevant IPD	Exclusion level
		
 
c. Subject who, in the judgment of the investigator, may be at risk for dehydration or volume depletion that may affect the interpretation of efficacy or safety data
 
d. Subject is currently abusing alcohol or other drugs or has done so within the last 6 months prior to screening
 
		
2.3	Did not fulfil eligibility criteria	
CV disorders
 
 
e. Uncontrolled hypertension defined as systolic blood pressure (SBP) <math>\geq 160</math> mmHg and/or diastolic blood pressure (DBP) <math>\geq 100</math> mmHg Note: Subjects with SBP <math>\geq 160</math> mmHg and <math>< 180</math> mmHg or a DBP <math>\geq 100</math> mmHg and <math>< 110</math> mmHg will be able to enter the open-label treatment period, provided their hypertension treatment is adjusted as deemed appropriate by the investigator. These subjects cannot be randomised if their BP remains SBP <math>\geq 160</math> mmHg or DBP <math>\geq 100</math> mmHg measured on Day 1.
 
f. Any of the following CV/Vascular Disease within 3 months of the screening visit, as assessed by the investigator: MI, coronary revascularization (percutaneous coronary intervention [PCI] or coronary artery bypass grafting [CABG]), unstable angina, Congestive heart failure as New York Association (NYHA) class III-IV (see Appendix C), angioplasty, valvular disease or repair, transient ischemic attack (TIA) or significant cerebrovascular disease, unstable or previously undiagnosed arrhythmia; or are expected to require PCI/CABG or angioplasty during the course of the study.
 
		

IPD code	IPD Category	Explanation	PP Relevant IPD	Exclusion level
		Subjects with stable cardiac disease are not excluded		
2.4	Did not fulfil eligibility criteria	
Renal Diseases
 
g. Subjects with moderate to severe renal impairment [defined as estimate glomerular filtration rate (eGFR) < 60mL/min/1.73 m^2 (estimated by MDRD) or serum creatinine (Scr) ≥ 1.5 mg/dL in males or ≥ 1.4 mg/dL in females] or end-stage renal disease (ESRD)
 
h. Unstable or rapidly progressing renal disease
 
i. Conditions of congenital renal glucosuria
		
2.5	Did not fulfil eligibility criteria	
Hepatic Diseases
 
j. Significant hepatic diseases, including, but not limited to, chronic active hepatitis and/or severe hepatic insufficiency and/or significant abnormal liver function, including subjects with Alanine aminotransferase (ALT) and/or Aspartate aminotransferase (AST) > 3x Upper limit of normal (ULN) and/or Total Bilirubin (TB) > 2x ULN
 
k. Subjects with severe hepatic impairment (Child-Pugh class C)
 
l. Positive serologic evidence of current infectious liver disease, including subjects who are known to be positive for hepatitis A viral (HAV) IgM antibody, hepatitis B surface antigen (HBsAg), and hepatitis C virus (HCV) antibody
		
2.6	Did not fulfil eligibility criteria	
Hematological/Oncological Diseases/Conditions
 
m. History of hemoglobinopathy, such as sickle cell anemia (SA), thalassemia or chronic or recurrent hemolysis, etc.
 
n. Malignancy within 5 years of the screening visit (with the exception of treated basal cell
	3. Randomised subjects with a history of haemoglobinopathy with the exception of sickle cell trait (SA) or thalassemia; or chronic recurrent haemolysis. (i.e.	Completely Exclude from PP analysis set

IPD code	IPD Category	Explanation	PP Relevant IPD	Exclusion level
		
or treated squamous cell carcinoma)
 
o. Known immunocompromised status, including but not limited to, individuals who have undergone organ transplantation or who are positive for the human immunodeficiency virus (HIV)
 
p. Donation of blood or blood products > 400mL or participation in a clinical study requiring withdrawal of > 400mL of blood during within 6 months prior to the screening visit
	violation of exclusion criterion #2m)	
2.7	Did not fulfil eligibility criteria	
Prohibited Treatment and Therapies
 
q. Administration of any anti-hyperglycemic therapy (other than metformin, or DPP-4 inhibitors, if applicable) for more than 14 days (consecutive or not) during the 8 weeks prior to screening
 
r. Any use of SGLT2 inhibitor within 8 weeks prior to screening
 
s. Prescription and over-the-counter weight loss medications within 3 months prior to screening
 
t. Current treatment with potent cytochrome P450 3A4/5 inhibitors (in countries where dose adjustment would be required by the saxagliptin label)
 
u. Administration of any other investigational drug or participation in any interventional clinical studies within 30 days prior to screening
		
2.8	Did not fulfil eligibility criteria	
Physical and Laboratory Test Findings
 
a. Hemoglobin (Hb) ≤ 11.0g/dL (110g/L) for men; Hb ≤ 10.0g/dL (100g/L) for women
 
b. For male subjects with microscopic hematuria urinalysis positive at screening
	4. Randomised Subjects with Abnormal free T4 values at enrolment (i.e. violation of exclusion criterion #3c).	Completely Exclude from PP analysis set

IPD code	IPD Category	Explanation	PP Relevant IPD	Exclusion level
		
and judged as clinically significant by the investigator will be excluded, but one re-test is allowed after resolution in the opinion of the investigator.
 
NOTE: Female subjects with hematuria can be randomised, but should be investigated according to local standards and best clinical practices.
 
c. Abnormal free thyroxine (T4) values. Abnormal thyroid stimulating hormone (TSH) value at screening will be further evaluated by free T4. Subjects with abnormal free T4 values will be excluded. Any clinically significant abnormalities in any pre-randomization lab analyses or ECG which in the investigator's opinion would preclude randomization
		
2.9	Did not fulfil eligibility criteria	
Allergies and Adverse Drug Reaction
 
History of any serious allergy/ hypersensitivity reaction to dapagliflozin, saxagliptin or to any of the excipients, including anaphylaxis or angioedema following exposure to any DPP-4 inhibitor
		
2.10	Did not fulfil eligibility criteria	Women who are pregnant or breastfeeding		
2.11	Did not fulfil eligibility criteria	
a. Subjects who are compulsorily detained for treatment of either a psychiatric or physical (e.g. infections disease) illness
 
b. Subjects on a commercial weight loss program with ongoing weight loss, or on an intensive exercise program
 
c. Subject with any condition which, in the judgment of the investigator, may render the subject unable to complete the study or which may pose a significant risk to the subject
		

IPD code	IPD Category	Explanation	PP Relevant IPD	Exclusion level
2.12	Did not fulfil eligibility criteria	
 
For subjects in Stratum A At Week -10 and Week -2 a FPG qualification check will be performed. Subjects with a central laboratory FPG value > 270 mg/dL will be scheduled for a follow-up visit (within 3 – 5 days following receipt of FPG value from central laboratory) to obtain a second central laboratory FPG value. If the mean of the originally scheduled central laboratory FPG and the repeat central laboratory FPG value is > 270 mg/dL, the subject cannot be randomised and must be discontinued
 
For subjects in Stratum B At Week -2 a FPG qualification check will be performed. Subjects with a central laboratory FPG value > 270 mg/dL will be scheduled for a follow-up visit (within 3 – 5 days following receipt of FPG value from central laboratory) to obtain a second central laboratory FPG value. If the mean of the originally scheduled central laboratory FPG and the repeat central laboratory FPG value is > 270 mg/dL, the subject cannot be randomised and must be discontinued
 
		
3. Did not discontinue Investigational product (IP) when discontinuation criteria (refer to CSP section 3.9.1) were met				
3.1	Subject decision	Subject decision. The subject is at any time free to discontinue treatment, without prejudice to further treatment		
3.2	AE/SAE related discontinuation	Subject experiences an AE or SAE that, in the investigator's opinion, necessitates discontinuation from study medication		

IPD code	IPD Category	Explanation	PP Relevant IPD	Exclusion level
3.3	Pregnancy	Pregnancy confirmed by a positive pregnancy test or otherwise verified		
3.4	Serious hypersensitivity	Serious hypersensitivity reaction		
3.5	Actue pacratitis	Acute pancreatitis		
3.6	Severe non-compliance	Severe non-compliance with the study protocol		
3.7	Loss of ability to freely provide consent	Loss of ability to freely provide consent through imprisonment or involuntary incarceration for treatment of either a psychiatric or physical (e.g., infectious disease) illness		
3.8	eGFR	eGFR < 60mL/min/1.73m  for sustained period of time (12 - 16 weeks) Note: Dapagliflozin based on its MOA has been shown to reduce eGFR by up to 10% with initiation of therapy; however, this has in general been reversible and not resulted in renal failure and eGFR values returned to baseline within 12 – 24 weeks of continued therapy.		
3.9	Hepatic function	Initial and repeat laboratory tests meet any of the following criteria: 
 
– ALT and/or AST are >3 x ULN and TB >2 x ULN
 
– ALT and/or AST are >5 x ULN for ≥14 consecutive days, at any time after initial confirmatory results
 
– ALT and/or AST are >8 x ULN
 
		
3.10	DKA	Consider to temporary interrupt dapagliflozin if DKA is suspected. The subject should be promptly evaluated. If DKA is confirmed, dapagliflozin should be discontinued permanently.		
3.11	Hypoglycaemia	Hypoglycaemia events as defined in CSP Section 3.9.2		
4. Concomitant & Other Study Medication Deviations				
4.1	Prohibited medications during the study	a. Randomised subjects who used anti-hyperglycemic therapy (other than protocol required medications) for ≥14 consecutive days during the	5. Randomised subjects who used anti-hyperglycemic therapy (other than protocol required	Partially exclude from PP analysis set (if occurs during double blind)

IPD code	IPD Category	Explanation	PP Relevant IPD	Exclusion level
		
open-label or double-blind period.
 
b. Randomised subjects newly initiating or changing treatment with systemic glucocorticoids for <math>\geq 5</math> days after enrolment
 
c. Randomized subjects receive potent cytochrome P450 3A4/5 inhibitor for <math>\geq 14</math> consecutive days during the open-label or double-blind period, without consultation between investigator and study physician.
	
medications) for <math>\geq 14</math> consecutive days during the open-label or double-blind period.
 
6. Randomised subjects newly initiating or changing treatment with systemic glucocorticoids for <math>\geq 5</math> days after enrolment
	
Completely exclude from PP analysis set (if occurs during open label)
 
5. Assess relevant deviation for subjects who are randomised. Assess the open-label and double-blind treatment periods together.
 
Exclusion would start from the 14th consecutive day that the medication is taken.
 
6. Assess relevant deviation for subjects who are randomised. Assess the open-label and double-blind treatment periods together. Change includes up or down titration.
 
Exclusion would start from the 5th day that the medication is taken.

4.2	Adjustment of background medication	Randomised subjects who took metformin $< 1500$ mg per day or adjusted from their maximal tolerated dose for $\geq 2$ consecutive weeks after enrolment	7. Randomised subjects who took metformin $< 1500$ mg per day or adjusted from their maximal tolerated dose for $\geq 2$ consecutive weeks after enrolment	
Partially exclude from PP analysis set (if occurs during double blind) Completely exclude from PP analysis set (if occurs during open label).
 
Assess relevant deviation for subjects who are randomised. Assess the open-label and double-blind treatment periods together. Exclusion would start from the 14th consecutive day that the medication is <math>< 1500</math>mg per day or adjusted from their maximal tolerated dose

IPD code	IPD Category	Explanation	PP Relevant IPD	Exclusion level
4.3	Saxagliptin treatment non-compliance	Randomized subjects who took no dose of saxagliptin for $\geq 2$ consecutive weeks of the days in the open-label or double-blind period	8. Randomized subjects who took no dose of saxagliptin for $\geq 2$ consecutive weeks of the days in the open-label or double-blind period	Partially exclude from PP analysis set (if occurs during double blind) Completely exclude from PP analysis set (if occurs during open label) Assess relevant deviation for subjects who are randomised. Assess the open-label and double-blind treatment periods together. Exclusion would start from the 14th consecutive day that saxagliptin was stopped.
4.4	Deviation of rescue treatment procedure	Subjects did not receive open label rescue medications when met rescue criteria		

